12.0 HUMAN SUBJECTS CONSIDERATIONS

12.1.2. Ethical Review

The protocol, ICF, participant education and recruitment materials, and other requested documents — and any subsequent modifications — will be reviewed and approved by the ethical review bodies responsible for oversight of research conducted at the study site. Subsequent to initial review and approval, the responsible IRBs/ECs will review the protocol at least annually.

12.1.3. Informed Consent

Written informed consent for screening and enrollment will be obtained from each study participant. Participants who are not literate will be read the informed consent document by a research staff member, in the presence of a literate, impartial witness (who will not be part of the study team). They will provider verbal consent and use a mark or thumbprint to indicate their consent. The consent will also be counter-signed by their witness. The ICFs describe the purpose of the study, the procedures to be followed, and the risks and benefits of participation, in accordance with all applicable regulations. The ICFs will be translated into a local language (isiZulu) and the accuracy of the translation will be verified by performing an independent back-translation. Participants will be provided with a copy of their ICFs if they are willing to receive them.

12.1.4. Risks

Sensitive Questions

Participants will be asked questions about their mental health and sexual behavior that may make them feel uneasy. Participants do not have to answer any question that they do not want to and can stop answering the questions at any time. Steps will be taken to minimize any psychological discomfort by providing ongoing counseling during study visits and as needed in between monthly sessions. We will also establish group norms prior to group counseling sessions to ensure that all participants feel comfortable during these group sessions.

Worsening symptoms of common mental disorders

Study participants may experience or more intense psychological discomfort during interviews or psychosocial counseling sessions due to disclosure about severe mental health symptoms or suicidal thoughts. The clinic has an on-site social worker and psychologist, who will be able to see more complicated participants either during their study visit or at a subsequent time. AGYW who report mental health distress related to gender-based violence or fears of violence will be provided referrals to meet with the on-site social worker and psychologist as needed. We will also provide participants with phone numbers to contact study staff after hours and information on how to report an issue to local police and law enforcement. We will follow Ward 21 standard operating procedures and South African Adult Primary Care Guidelines for responding to issues of acute mental distress among AGYW. AGYW who report a history of suicide attempt and/or current suicidal ideation or intent during the study (assessed via three questions routinely used for screening and linkage to care in this study setting) will immediately be linked to further care as needed.

Confidentiality

Although the study site will make every effort to protect participant privacy and confidentiality, it is possible that participants' involvement in the study could become known to others, and that social harms may result (e.g., because participants could become known as at "high risk" for HIV infection). For example, participants could be treated unfairly or discriminated against, or could have problems being accepted by their families and communities. We will establish group
norms prior to group counseling sessions to ensure that all participants are aware of the need to protect one another's confidentiality. Participants who are concerned about confidentiality may choose to use a pseudonym when participating in group counseling sessions and all group session attendees will be encouraged to refrain from discussing other participants with friends and families. We will remind participants prior to individual and group sessions that they can leave the session or decline to participate at any time. Lists of referrals are in place to address recent psychological problems needing intervention and the study site has a social worker and clinical psychologist available on site to address any pressing participant needs. All research staff are rigorously trained and all intervention activities and data collection will take place in private rooms with closed doors.

Confidentiality and data storage concerns for SMS reminder messages

Participants will be offered optional SMS appointment reminders. The SMS platform used for participant text messaging is end-to-end encrypted, meaning only members of the study team can access it. The SMS platform will be accessed by study staff through a password-protected laptop, stored in a locked office. All data records will be identified by study ID only. The link between identifiable participant information and study IDs will be locked in a secure location and destroyed following study completion. There is some potential risk of confidentiality loss associated with having sensitive SMS messages with appointment reminders or communication with healthcare staff stored on participants' personal phones. We will ensure all prospective participants review example SMS messages so that they are aware of the content of SMS they will receive as part of informed consent procedures. All participants will be informed that their participation is voluntary and can stop receiving the SMS messages at any time by texting "STOP" which will cease on SMS communication between study staff and the participant. All study staff will be trained in protection of human subjects and the clinical and emotional needs of AGYW with symptoms of common mental disorders on PrEP.

Confidentiality and data storage concerns for remote visits

Participants will be offered optional remote counseling sessions (via telephone). The lay counselor will confirm readiness for remote visits by phone to ensure the participant safety and confidentiality. Remote visit procedures will be detailed in a standard operating procedure. Remote sessions will not be recorded and no identifiable data about the session will be stored. All participants will be informed that their participation is voluntary and they can stop the remote session at any time. All study staff will be trained in protection of human subjects and the clinical and emotional needs of AGYW with symptoms of common mental disorders on PrEP.

12.1.5. Benefits

There may be no direct benefits to participants in this study beyond the provision of counseling and referrals; however, participants and others may benefit in the future from information learned from this study. Specifically, information learned in this study may help to prevent common mental disorders, HIV, and other infections.

12.1.6. Compensation

Pending IRB/EC approval, participants will be compensated for their time and effort in this study (beyond standard-of-care service delivery) at enrolment, week 4 and week 12 study visits. Reimbursement amounts will be specified in the study informed consent forms (ICFs). Participants in the Youth Friendship Bench SA arm who complete a virtual group session between their Week 8 and 12 visits will be provided 2GB data prior to the start of the session.

12.1.7. Study Records

All study-related records including administrative documentation and regulatory documentation as well as documentation related to each participant enrolled in the study, including informed consent forms, locator forms, case report forms, notations of all contacts with the participant, and all other source documents are stored in a secure manner at the study site.

12.1.8. Confidentiality

The study site will establish a standard operating procedure for confidentiality protection. All participant information will be stored in locked file cabinets in areas with access limited to study staff. All DBS cards, reports, study data collection, process, and administrative forms will be identified by a coded number only to maintain participant confidentiality. All local databases will be secured with password-protected access systems. Forms, lists, logbooks, appointment books, and any other listings that link PTID numbers to other identifying information will be stored in a separate, locked file in an area with limited access.

Staff will use a code word prior to each text message (similar to Weltel)¹²⁴ to prevent inadvertent disclosure of study participation in the case of shared mobile phones. Staff will not be able to access any information on participants' mobile phones.

Participants' study information will not be released without their written permission, except as necessary for oversight by:

- The Protocol Chair or designees
- Study funders
- Site IRB/ECs
- University of California San Francisco
- Any additional study sponsors

- 122. Fitzpatrick, R. & Boulton, M. Qualitative methods for assessing health care. Qual. Health Care QHC 3, 107–113 (1994).
- Leonard, K. & Masatu, M. C. Outpatient process quality evaluation and the Hawthorne Effect. Soc. Sci. Med. 1982 63, 2330–2340 (2006).
- 124. Lester, R. T. *et al.* Effects of a mobile phone short message service on antiretroviral treatment adherence in Kenya (WeITel Kenya1): a randomised trial. *Lancet Lond. Engl.* **376**, 1838–1845 (2010).
- 125. Cherian, V. I., Peltzer, K. & Cherian, L. The factor-structure of the Self Reporting Questionnaire (SRQ-20) in South Africa. *East Afr. Med. J.* **75**, 654–656 (1998).
- 126. van der Westhuizen, C., Wyatt, G., Williams, J. K., Stein, D. J. & Sorsdahl, K. Validation of the Self Reporting Questionnaire 20-Item (SRQ-20) for Use in a Low- and Middle-Income Country Emergency Centre Setting. Int. J. Ment. Health Addict. 14, 37–48 (2016).

Appendix 1: Standard-of-care assessment of common mental disorders for patients seeking primary or HIV care, according to the South African Adult Primary Care Guidelines¹⁰⁸

- 1. In the past month, has the patient felt down, depressed, or hopeless? (Yes, No)
- 2. In the past month, has the patient felt little interest or pleasure in doing things? (Yes,
 - No)

If yes to either, then assess whether patient has had 5 or more of the following features for the last 2 weeks:

- Depressed mood most of the day, nearly every day
- Loss of interest or pleasure in activities that are usually pleasurable
- Fatigue or loss of energy
- Disturbed sleep or sleeping too much
- Change in appetite or weight
- Feeling guilty or worthless
- Reduced concentration or indecisiveness
- Visible agitation or restlessness, or talking or moving more slowly than usual
- · Ideas or acts of self-harm or suicide

Appendix 2: Self-reporting questionnaire, 9-item (SRQ-20) for screening common mental disorders^{125,126}

- 1. Do you often have headaches?
- Is your appetite poor?¹
- 3. Do you sleep badly?1
- 4. Are you easily frightened?
- 5. Do your hands shake?1
- 6. Do you feel nervous, tense, or worried?
- 7. Is your digestion poor?1
- 8. Do you have trouble thinking clearly?1
- Do you feel unhappy?¹
- 10. Do you cry more than usual?
- 11. Do you find it difficult to enjoy your daily activities?1
- 12. Do you find it difficult to make decisions?1
- 13. Is your daily work suffering?1
- 14. Are you unable to play a useful part in life?1
- 15. Have you lost interest in things?1
- 16. Do you feel that you are a worthless person?1
- 17. Has the thought of ending your life been on your mind?^{1,2}
- 18. Do you feel tired all the time?1
- 19. Do you have uncomfortable feelings in your stomach?
- 20. Are you easily tired?1

¹Item corresponds with factors to be assessed in the Adult Primary Care guidelines for standard-of-care mental health assessment and will be used to determine somatic symptoms that require additional care and possible referral by a social worker.

²Participants who endorse this item will be asked three additional questions to determine suicide intent and self-harm: 1) Do you ever have thoughts of hurting or killing yourself?; 2) Are you currently thinking of killing yourself?; 3) Have you ever tried to kill yourself?. Endorsement of any of these items will result in linkage to care and the AGYW will not be eligible for participation in the study until acute self-harm issues are resolved.

Session ²	Overview of content to be covered			
Session 1 (9 AM – 5PM)	Background information on common mental disorders including symptom profiles and how to recognize them Psychoeducation on mental health Screening using the SRQ-20 Practice with the SRQ-20 Overview of counseling skills and problem-solving therapy Referral procedures Overview of supervision plans Collecting and reporting client data for study purposes Creating awareness of mental health and understanding community stigma and stigma reduction approaches Practicing skills from the day			
Session 2 (9 AM – 5PM)	 Overview and practice of first session with Youth Friendship Bench SA client Continued discussion of problem-solving therapy, including how to work with a client to select and define a problem Emotion regulation approaches for client management Prioritizing one problem for Youth Friendship Bench SA sessions Approaches to brainstorm solutions for the problem with clients Practicing skills from the day 			
Session 3 (9 AM – 5PM)	 Creating a "safe space" for Youth Friendship Bench SA clients Approaches to select appropriate and actionable solutions with clients S.M.A.R.T. goals and developing an action plan Recording information in the research records Practice skills from the day Practice receiving feedback from supervisors and study team members 			
Session 4 (9 AM – 5PM)	 Review of problem-solving therapy practice session Mental health literacy for working with adolescent girls and young women Psychoeducation: depression Psychoeducation: grief Psychoeducation: anxiety Psychoeducation: panic disorders Psychoeducation: post-traumatic stress disorder Psychoeducation: alcohol and drug use Psychoeducation: suicide and self-harm Approaches for linking patients to care for issues of self-harm, suicidal ideation, or suicidal intent 			

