7.3.3. Exclusion Criteria

Young women who meet any of the following criteria will be excluded from enrolling in this study:

- Not on PrEP and/or not intending to use PrEP for the duration of the study
- Planning to relocate in the next three months
- Report of suicidal intent or self harm
- Active, unmanaged mental health disorders, including untreated or severe somatic symptoms and active psychiatric symptoms (e.g., hallucinations)
- Reactive or positive HIV test at enrollment (based on clinic records only; we will not perform HIV testing under this protocol)

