8.3.2. Screening and Enrollment Visit

The screening and enrollment visit may be conducted as a split visit as needed. Young women who are eligible and agree to study participation will be consented for 3 months of follow-up. The following procedures will take place:

- 1. Review and obtain written informed consent.
- 2. Confirm/Record locator information and phone number and contact preferences.
- 3. Assign a unique study identification number
- Assess eligibility (e.g., age 18-25 years, newly initiating PrEP at the clinic, symptoms of common mental disorders), including Adult Primary Care Guidelines screening questions and the SRQ-20
 - a. If participants report suicidal ideation or intent, have untreated or severe somatic symptoms or have other active psychiatric symptoms (e.g., hallucinations) the participant will be referred for assessment by a trained health professional (see Section 4.2).

Participants that are already on treatment with stable symptoms may continue to randomization.

- 5. Offer enrolment to eligible participants and refer ineligible for additional services if needed.
- Collect additional data on past mental history, participation in other mental health or HIV interventions, and other psychosocial and behavioral data (see Section 6).
- 7. Randomize participant to either Youth Friendship Bench SA intervention or the standard-of-care condition.
 - a. Participants randomized to the Youth Friendship Bench SA intervention will complete their first counseling session at this visit.
 - i. Collect preferences for SMS appointment reminders (see Section 4.3)
 - ii. Schedule participant for their Week 2 visit in 14 days. They will be offered the option to complete the Week 2 visit in-person or remotely (over the phone).
 - Standard-of-care participants will be scheduled for their next clinic visit at Week 4 in 30 days. They will not receive appointment reminders or remote services.

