psychotherapy or pharmacotherapy as needed. We will also inform these AGYW that they can continue to receive PrEP at the study clinic.

Suicidal ideation, regardless of SRQ-20 score: The SRQ-20 includes one question on suicidal ideation ("Has the thought of ending your life been on your mind"), and anyone who endorses this item (regardless of their total SRQ-20 score) will be asked a series of three additional questions to determine suicidal intent ("Do you ever have thoughts of hurting or killing yourself?", "Are you currently thinking of killing yourself?", "Have you ever tried to kill yourself?"). They will also be provided referral to a social worker for further support as needed. Anyone who expresses suicidal intent or is deemed a risk to themselves or others will be ineligible for participation and immediately linked to inpatient care. They will only be able to re-screen into the study if and when their symptoms have stabilized and they not longer report self-harm or suicidal intent.

Worsening symptoms of common mental disorders throughout study follow-up: All participants will be asked whether their symptoms of common mental disorders have changed during the Week 4 and 12 visits and they will also complete the SRQ-20 at these time points. We will follow similar procedures as described for items a-c above, to ensure that individuals are linked with standard-of-care services regardless of SRQ-20 score. Those with symptoms of severe mental health distress or psychosis (e.g., unmanaged somatic symptoms, suicidal intent) will be linked to care and the study team will consider early termination from the study on a case-by-case basis.

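### The Protocol gives two different entry rules for the same three suicidality questions: Appendix 2 bars entry on any yes, while Section 9.1 bars entry only on intent or judged risk.

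*Protocol*

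**What the plan says.** Four places in the Protocol bear on entry.

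- **Appendix 2, footnote 2.** A woman who endorses SRQ-20 item 17 (thoughts of ending her life) is asked three more questions: whether she ever has thoughts of self-injury or suicide, whether she has suicidal thoughts now, and whether she has ever made an attempt. The consequence is: "Endorsement of any of these items will result in linkage to care and the AGYW will not be eligible for participation in the study". The sentence then limits this to the period until the acute self-harm problem is resolved.
- **Section 9.1, paragraph on suicidal ideation** (under the subheading on mental health symptoms). The trigger and the three questions are the same. On referral it says: "They will also be provided referral to a social worker for further support as needed". On entry it says: "Anyone who expresses suicidal intent or is deemed a risk to themselves or others will be ineligible for participation". Re-screening is allowed once symptoms have stabilized and neither self-harm nor intent is reported any longer.
- **Section 7.3.3, exclusion criteria.** The criterion is "Report of suicidal intent or self harm", with no time frame.
- **Section 8.3.2, step 4a.** The step opens "If participants report suicidal ideation or intent, have untreated or severe somatic symptoms or have other active psychiatric symptoms", and the stated consequence is that "the participant will be referred for assessment by a trained health professional". It adds: "Participants that are already on treatment with stable symptoms may continue to randomization".

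The SAP (Study Design) says only that participants must meet all inclusion criteria and no exclusion criteria, so it does not settle the matter.

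**The concern.** Appendix 2 and Section 9.1 start from the same item and ask the same questions, yet a woman who answers yes to some of them may be not eligible under one and eligible with a referral under the other. The Protocol does not say which passage takes precedence.

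This rule is a safety screen, applied to women selected for distress (SRQ-20 of 7 or more). The lay counselors administer the SRQ-20 (Section 10.1) after a one-week training (Section 8.2), so they need a rule that can be applied as written. If staff use different passages, the same answers lead to different entry decisions, eligibility deviations cannot be judged consistently, and the range of baseline severity among those enrolled depends on the page consulted.

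**Working it through.** No sample size or power figure is involved. The check sets the passages against each other for every possible set of answers.

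**Inputs.** Among women who endorse item 17, let A be thoughts of self-injury or suicide at any time (no time window in the item), B current suicidal thoughts, and C any lifetime attempt. Each is yes or no, so there are 2 × 2 × 2 = 8 answer patterns.

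**Assumption.** Intent means yes to B. The Protocol does not map answers to intent.

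| A | B | C | Appendix 2, footnote 2 | Section 9.1 | Section 7.3.3 |
|---|---|---|---|---|---|
| no | no | no | not barred | referred, not barred* | not barred |
| yes | no | no | **barred** | **referred, not barred*** | not clearly reached |
| no | no | yes | **barred** | **referred, not barred*** | depends on whether a past attempt is self-harm |
| yes | no | yes | **barred** | **referred, not barred*** | depends on whether a past attempt is self-harm |
| any | yes | any (4 patterns) | barred | barred | barred |

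*Unless she is judged a risk to herself or others.

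**Counts.**
- Appendix 2 bars any yes: 8 − 1 = 7 patterns.
- Section 9.1 bars B = yes: 4 patterns, plus anyone judged a risk.
- Appendix 2 and Section 9.1 disagree on 7 − 4 = 3 patterns: A only, C only, and A with C.
- Section 7.3.3 bars 4 patterns. If an undated report of self-harm includes a past attempt, it bars 6 (all except the two with B = no and C = no). On either reading it differs from Appendix 2 on at least one pattern, A only, since 7 − 6 = 1.

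**Clearest example.** A woman says yes to item 17 and yes to A, but no to B and C. She is not eligible under Appendix 2. Under Section 9.1 she is referred and not excluded unless judged a risk. Section 7.3.3 does not clearly reach her, because she reports thoughts without current intent or any act.

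**The time qualifier.** Appendix 2 lifts the bar when acute issues resolve, but does not say how this works where nothing is acute. A yes to a lifetime-attempt question stays a yes, so the footnote leaves open whether a remote attempt bars entry, defers it, or has no effect once nothing acute is found.

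**Section 8.3.2.** This step prescribes referral and never says ineligible. On ideation its referral agrees with Section 9.1. It touches entry only by implication, through the sentence on who may go on to randomization. Its cross-reference is to Section 4.2, the number Section 7.1 uses for counselor training. The matching text, now Section 8.2, contains no suicidality rule.

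**The case against.** The strongest reply is that the passages form layers. Section 7.3.3 states the criterion, the three questions put it into practice (both Section 9.1 and Appendix 2 say they are asked to establish intent, and Appendix 2 adds self-harm), and the judged-risk clause leaves room for clinical judgment. If any yes counted as intent, Section 9.1 and Appendix 2 would agree. This reading is possible, but no passage states it. Section 8.3.2 names ideation and intent separately, and Section 12.1.4 lists attempt history, ideation and intent as distinct. The gap is therefore real as the text stands, although it could be closed by writing the mapping down.

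A second reply also carries weight: Appendix 2 describes a deferral, Section 9.1 also allows re-screening, and women with a positive screen are referred or linked to care on every reading. That limits the consequence. It does not remove the conflict over whether a woman may enter at that visit.

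A reader might infer several stronger things that the documents do not support:

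- **Four rival exclusion rules.** Section 8.3.2 is a referral step, and the passage in Section 12.1.4 concerns management during the study.
- **Every woman with a past attempt is affected.** Under Section 9.1 and Appendix 2, only those who endorse item 17 are asked the three questions.
- **Women with current intent could be enrolled.** Intent bars entry under Sections 7.3.3 and 9.1, and current suicidal thoughts bar it under Appendix 2.
- **The arm comparison of self-harm events is biased.** Eligibility is settled at step 4 of Section 8.3.2 and randomization follows at step 7, so inconsistent screening does not by itself favor either arm.

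**Conclusion.** The contradiction between Section 9.1 and Appendix 2 holds, and Section 7.3.3 does not resolve it. With intent read as current thoughts, the two rules give different entry decisions for 3 of 8 answer patterns. For the pattern with past or occasional thoughts only, Appendix 2 also departs from Section 7.3.3 however self-harm is read. The lifetime-attempt pattern is a weaker example against Section 7.3.3, because undated self-harm could include it.

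The patterns are not equally common, so 3 of 8 is not a share of women. The documents give no prevalence for any of these answers, and the number affected cannot be derived. What is at stake is consistent safety screening and a well-defined enrolled population. The validity of the randomized comparison is not affected.

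**What to change.** Reconcile Section 7.3.3, Section 9.1 and Appendix 2, footnote 2 into one entry rule, stated once and referred to elsewhere. For each of the three questions it should give the consequence for entry and the time frame that applies. It should define what is meant by intent and by self-harm, and say how the resolution clause works when nothing is acute. Align the wording of Section 8.3.2, step 4a with that rule and correct its cross-reference. The clinical team decides the content; this review takes no position on which rule is right.

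The cost is a protocol clarification, ethics notification and brief re-training of screening staff. No new procedure or data collection is needed.
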